## ABBREVIATIONS

AE	Adverse Event
AV	Adelphi Values
CD	Cognitive Debriefing
CE	Concept Elicitation
COA	Clinical Outcomes Assessment
CRF	Case Report Form
ENT	Ear, Nose and Throat
GSK	GlaxoSmithKline
HRQoL	Health-Related Quality of Life
ICF	Information Consent Form
PRO	Patient-Reported Outcome
SNOT	Sino-Nasal Outcomes Test
US	United States
VAS	Visual Analogue Scales

## 1 INTRODUCTION/BACKGROUND

Nasal polyps is considered to be a subgroup of chronic rhinosinusitis and is defined as a chronic inflammatory disease of the nose and sinuses. Nasal polyps is characterized by the presence of two or more of the following symptoms: watery rhinorrhea from the nose (anterior), postnasal drainage (posterior), nasal obstruction and a temporary or in extreme cases permanent decreased sense of smell (anosmia). The standard of care for patients with severe nasal polyps includes intranasal steroids, oral corticosteroids and surgery. However, there are currently no established criteria for surgery; candidacy for surgery is considered on the basis of level of nasal obstruction, symptom severity, impacts to the patient and the perceived risks/benefits of surgery.

The patient experience of nasal polyps is typically assessed via clinical interview and review of clinical history and the use of existing patient-reported outcome instruments (PROs). PRO instruments used with patients with nasal polyps typically include single item visual analogue scales (VAS), whereby patients are asked to evaluate overall symptom severity, or the severity of individual symptoms of nasal polyps along a continuum, typically of 10cm or 100 mm whereby 0 represents 'no symptom' and '10 or 100 represents 'as bad as you can imagine', Scores of 0-3 (or 0-30) are defined as mild disease, >3-7 (or >30-70) as moderate disease and >7-10 (or >70-100) as severe disease. Historically, these items have not been developed based on patient characterization and therefore there is a need to understand the appropriateness of these measures for use within this population. The Sino-Nasal Outcomes Test (SNOT-22) is also used frequently within clinical research and as a clinical trial endpoint to measure health-related quality of life associated with rhinosinusitis with or without nasal polyps. The SNOT-22, a derivative of the SNOT-20, is a modification of the 31-Item Rhinosinusitis Outcome Measure (RSOM), containing 22 nose, sinus, and general health-related quality of life (HRQoL) items. Within the SNOT-22 patients are required to indicate the level of to which each listed nasal, sinus or HRQoL experience has been affected on a 6-point scale ranging from 0 (No problem) to 5 (Problem as bad as it can be) and also identify the five most important items affecting their health. Existing evidence supports the psychometric validity of the SNOT-22 among patients with rhinosinusitis; with evidence of high reliability and sensitivity to clinical change. Preliminary searches, however, suggest that evidence regarding the content validity of the SNOT-22 may be lacking.

GlaxoSmithKline (GSK) is embarking on a clinical program to assess treatment of severe, recurrent nasal polyps with an anti-interleukin-5 (anti-IL5) (mepolizumab). Patient symptomatic endpoints will form the basis for the assessment of treatment benefit of nasal polyp therapies. Currently, there is a lack of published qualitative data regarding nasal polyps to understand the symptoms (specific symptoms, duration,

frequency, severity) or health-related quality of life (HRQoL) impacts for patients, as well as the patient decision-making process in electing for surgery and their pre- and post-surgical experience to treat nasal polyps. In line with regulatory requirements, the patient experience of nasal polyps will need to be characterized. Additionally, as described above, there is a requirement to evaluate existing symptomatic endpoints with respect to relevance and comprehensiveness within this population to inform GSK's clinical outcome assessment (COA) strategy for this trial.

To address this unmet need GSK would like to conduct a qualitative research study with adult patients with nasal polyps to explore the disease experience from the patient perspective and to debrief existing symptomatic PROs (including overall and single item VAS's and the SNOT-22), via patient interviews and real-time data capture. This protocol details the methods and procedures that will be used in the conduct of this study.

## **2 OBJECTIVES**

### **2.1 Primary**

To explore the symptom, impact and surgery experience of patients with severe, recurrent nasal polyps and obtain patient feedback regarding the adequacy of the SNOT-22 and GSK VAS assessments (in terms of relevance and comprehensiveness) in assessing disease experience in nasal polyps.

### **2.2 Secondary**

#### **Combined concept elicitation (CE) and cognitive debriefing (CD) interviews:**

To identify through open-ended questioning the concepts that are important to patients with severe, recurrent, nasal polyps, who have been treated with surgery and the language they use to describe their disease experience. The main areas of exploration will be the symptoms with particular attention paid to the frequency, severity, duration and bother of each symptom, patients' surgical decision-making and surgical/treatment experience and the functional and HRQoL impact experienced by patients.

To cognitively test and explore the content and face validity of existing PRO instruments (single item VAS and SNOT-22) via assessment of the relevance and appropriateness of the items included in the instruments and the participants' ability to read, and consistently understand the instrument item wording, instructions, response option and recall period. The CD interviews will:

- Explore participants' ability to read and consistently understand the item wording, instructions, response options and recall period of the overall and single item VAS and SNOT-22.
- Explore the relevance and appropriateness of all of the items covered by the instruments based on the symptom experience of patients with nasal polyps.
- Verify if the key concepts identified in the concept elicitation phase of the study are adequately assessed by the PRO instruments (confirmation of face validity) and if any gaps exist, provide recommendations for how these could be addressed.
- Explore what level of change in symptoms and/or impacts the patients might consider meaningful. (E.g. what level of change they might consider noticeable and important in response to treatment, and how changes on the item scores might relate to changes in their experience in their symptoms and/or functional impacts.

**Real-time data capture application:**

To supplement the CE section of the interviews with additional data regarding the patient experience of nasal polyps in 'real time' using smartphone/tablet app based technology. Real-time data capture uses a smart-phone or web-based application allowing the patient to communicate about their experience of nasal polyps in real-time as they go about their daily lives via varying video, audio, photographic and text responses.

Real-time data capture will be used to field a series of questions/tasks to patients with nasal polyps to:

- Explore the patient experience of the symptoms, HRQoL impacts and treatment of nasal polyps and any day-to-day variability that exists in these experiences in 'real time'.

Note: This is a low-interventional study – participants will not be asked to change their treatment as part of this study.

### **3 RESEARCH METHODOLOGY**

#### **3.1 Study Design**

This is a cross-sectional qualitative study comprising the conduct of semi-structured combined CE and CD telephone interviews (each 120 minutes in duration) conducted in with US and German adults with severe, recurrent nasal polyps. In addition to the interview, the study includes a real-time data capture task conducted with US participant only over a 10-day period using smartphone/tablet app-based technology. The combined CE and CD interviews aim to investigate the patient experience of nasal

polyps, and the relevance and understanding of existing PRO instruments (e.g. VAS and SNOT-22).

A total of 20 adult participants from the US with severe, recurrent, nasal polyps, who have received nasal polyp removal surgery in the past 10 years, will participate in the study as well as 10 patients of the same characteristic in Germany. In qualitative research, sample size estimation is based on projections of the number of participants needed to reach conceptual saturation (i.e., the point in the data collection process after which no new information is elicited). Past evidence in the literature suggests that conceptual saturation can be achieved in as few as 12 individual interviews in a relatively homogenous population. As such, it is anticipated that conceptual saturation will be achieved within 20 interviews.

This study comprises two qualitative research activities outlined in the sections below: combined CE and CD qualitative interviews and real-time data capture.

#### **Combined CE and CD interviews (120 minutes)**

Twenty participants for the US and 10 from Germany (total sample= 30 participants) will be invited to part in combined CE and CD interviews. The CE component of the interview will explore participants' experience of living with severe, recurrent nasal polyps with particular focus on participants' symptoms, impacts and treatment/surgical experiences relating to their condition and the terminology used to describe their experiences. Following CE, participants will complete the CD component of the interview. Participants will complete the existing PRO instruments (overall symptom VAS, single item VAS and SNOT-22) as part of a 'think aloud' process in which they will be asked to speak aloud their thoughts as they read the instructions and complete the questions. Participants will also be probed upon their experience of completing the instruments/items and the relevance and participant understanding of the instrument items, instructions, recall period and response options. Further details regarding the conduct of the combined CE and CD interviews are provided in section 3.3.

#### **Real-time data capture application (10 days)**

All 20 US patients will be invited to take part in an app-based real world data capture activity. It is anticipated that of the 20 interview participants, a sub-set of ten will meet the inclusion criteria for this task. Therefore, the first ten patients to meet the criteria will make up the sample for this task. Five of the ten participants (50%) will take part in the app task prior to their interview and the remaining five participants (50%) will take part in the app task following their interview. Using this methodology, identified participants will be asked to download an app to their smartphone or tablet. Data capture will be conducted over a 10 day period and during this time participants will receive a series of questions/tasks via the application that they can response to in real-time, designed to

explore the experience of nasal polyps. The task will aim to explore the patient experience of the symptoms, HRQoL impacts and treatment of nasal polyps and any day-to-day variability that exists in these experiences in 'real time'. Participants will be able to provide responses to the questions/tasks fielded to them using a variety of methodologies including video, audio, text and photographic responses with captions. Further details regarding conduct of the real-time data application component are provided in section 3.3.

### **3.2 Study Population**

Twenty adult participants in the US, and 10 participants in Germany with severe, recurrent nasal polyps who have received nasal polyp surgery in the past 10 years prior to screening will take part in this study. Of these 30 participants, 10 of the 20 US participants (50%) will also complete the real-time data capture app task. The real-time data capture app task will not be conducted in Germany.

MedQuest Global, a recruitment agency, will assist in recruiting participants from a minimum of two geographically diverse sites in the US (e.g., East Coast, West Coast, Southern states). Zeste, a recruitment agency in Germany will assist with the recruitment of the German sample across 1-2 sites. Both agencies will recruit participants using the same methodology outlined below.

Participants will be recruited through a combination of primary care physicians/general practitioners and ear, nose and throat (ENT) specialists. Physicians will identify suitable participants for the study using the case report form (CRF) (Appendix 4). Participants identified by their physician will be provided with two copies of the information and consent form (ICF) to read and sign to indicate informed consent/assent if they wish to participate in the study (Appendix 5) – one for the participant to keep and one that the recruitment agency will send to AV. Participants will be given the opportunity to consider the information provided in the ICF and to ask the recruitment agencies/recruiting physician or AV any questions about the ICF before providing their informed consent. If the participant verbally agrees to take part and also signs the ICF, they will be informed that their name and contact information will be passed to the respective recruitment agencies in each country who will contact them to screen them into the study and collect demographic information about each participant (Appendix 6), ensuring study quotas are met for obtaining a representative sample as outlined in section 3.2.2. No information will be passed to the recruitment agencies until verbal and informed consent has been obtained from the participant. After informed consent has been obtained, the participant's physician will release the CRF data to the respective recruitment agencies in each country (Appendix 4); confirming that the participant meets the study inclusion requirements, and providing additional information about the participant's clinical condition and medical history. MedQuest Global will be responsible for ensuring that

any US participant who opts in to take part in the real-time data capture activities meets the criteria as outlined in section 0.

If the participant meets the criteria for inclusion in the study section 3.2.1.1 the recruiter will organize enrolment into the app task (where applicable) and schedule a time for the participant to attend the 120-minute interview visit. Of the 10 US participants who elect to take part in the app task five will complete the app task prior to their scheduled interview, and the remaining five will complete the app task after their interview. For the five US participants who complete the app task prior to their interview they will be asked about their experience of completing the app task at the end of the interview. For the five US participants who complete the app task after their interview, a separate a brief telephone call (approximately 5-10 minutes) will be scheduled with the participant to ask them brief questions about their experience. The questions relating to the participant experience of completing the app task are provided in Appendix 7.

In terms of compensating participants for their involvement in the study the following compensation structure will be employed:

#### **Payments to participants for their participation**

US participants will receive \$200 upon completion of the 120-minute interview. Those participants who also complete real-time data capture will receive an additional payment of \$200. German participants will each receive €200 following completion of the interview. All payments will be paid via bank transfer or amazon voucher.

### **3.2.1 Eligibility Criteria**

Participants eligible for enrolment in the study must meet the following inclusion and exclusion criteria, which are broadly reflective of GSK's clinical trial population.

#### **3.2.1.1 Inclusion Criteria**

Participants will be required to meet the following inclusion criteria to be eligible for inclusion in the study.

1. Participant has a clinical diagnosis of **bilateral nasal polyps** as diagnosed by endoscopy or CT scan;
2. Participant is aged 18 or over;
3. Participant has severe nasal polyps symptoms defined as a patient-reported nasal obstruction VAS score of >5 (Appendix 1);
4. Participant has had at least **one previous surgery in the past ten years** for the **removal of nasal polyps**. Surgery in this case is defined as any procedure involving instruments with resulting incision and removal of polyp tissue from the nasal cavity (polypectomy);

5. Participant is currently an eligible candidate for polypectomy defined by:

a) An overall patient-reported VAS symptom score of  $>7$ . (**Appendix 2**), **AND**

An endoscopic bilateral nasal polyp score of at least 5 out of a maximum score of 8 (with a minimum score of 2 in each nasal cavity). (

- b) Appendix 3);
- 6. Participant has symptoms consistent with chronic rhinosinusitis;
- 7. Participant is currently received intranasal corticosteroids for the management of their nasal polyps;
- 8. Participant is willing to participate in the study and provide informed consent;
- 9. Participant is an English speaker and is able to read, write and fully understand the English language;
- 10. Participant is willing to and able to attend and participate in a 120-minute interview to discuss their experiences of nasal polyps and obtain their feedback on several symptom/impact questionnaires.

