	
To identify through open-ended questioning the concepts that are important to patients with severe, recurrent, nasal polyps, who have been treated with surgery and the language they use to describe their disease experience. The main areas of exploration will be the symptoms with particular attention paid to the frequency, severity, duration and bother of each symptom, patients' surgical decision-making and surgical/treatment experience and the functional and HRQoL impact experienced by patients.
 
Cognitive debriefing objectives:
 
To cognitively test and explore the content and face validity of existing PRO instruments (single item VAS and SNOT-22) via assessment of the relevance and appropriateness of the items included in the instruments and the participants' ability to read, and consistently understand the instrument item wording, instructions, response option and recall period.
 
Real-time data capture app
 
To explore the patient experience of the symptoms, HRQoL impacts and treatment of nasal polyps and any day-to-day variability that exists in these experiences in 'real time' using smartphone/tablet app based technology.

Study Design	
This is a cross-sectional qualitative study comprising the conduct of semi-structured combined CE and CD telephone interviews (each 120 minutes in duration) with US (n=20) and German (n=10) adults with severe, recurrent nasal polyps. The combined CE and CD interviews aim to investigate the patient experience of nasal polyps, and the relevance and understanding of existing PRO instruments (e.g. VAS and SNOT-22). In addition to the interview, the study includes a real-time data capture task conducted with 10 of the 20 US participants over a 10-day period using smartphone/tablet app-based technology. Five of the ten participants (50%) will take part in the app task prior to their interview and the remaining five participants (50%) will take part in the app task following their interview.
 
This study will be conducted by Adelphi Values, an independent research agency specializing in health outcomes research, on behalf of GSK.

Study Population and Sampling Methods	
A sample of 20 US-English speaking patients and 10 German patients will be recruited, giving a collective sample of 30 patients. Recruitment will be facilitated by third-party vendors in

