
Data Source
	
This study will consist of combined concept elicitation and cognitive debriefing interviews, which will last for 120 minutes in total. All participants (20 participants from the US and 10 participants from Germany) will all complete these interviews. Ten of the 20 US participants (50%) will also complete a 10-day real-time data capture app task and provide feedback about their experience of completing this task.
 
No endpoints are specified or feature as part of this study.

Data Analysis Methods
	
Descriptive socio-demographic and clinical characteristics  Socio-demographic and clinical characteristics for participant collected from the demographics form and CRF respectively will be summarized using descriptive statistics (e.g. n vales, means, ranges, percentages etc. where relevant).
 
Analysis of interviews  All interviews will be audio-recorded, and along with audio real-time data capture app task responses, transcribed/translated verbatim. Transcripts will be analyzed using thematic analysis methods and qualitatively coded using Atlas.Ti software. The Adelphi Values project team will create the initial code list, and each transcript would be assessed and participant comments that pertain to the main research questions would be highlighted. The code list will be updated iteratively during the coding process. The CE interview data will be analyzed in accordance with the principle of conceptual saturation as fully outlined in section 4.
 
Descriptive statistics for the SNOT-22 and visual analogue scales  The data collected from the SNOT-22 and visual analogue scales during the CD interview will be scored by Adelphi Values and summarized using descriptive statistics (e.g., n values, mean scores, ranges and percentages). Information relating to the distribution of responses will be summarized in addition to any missing data. The data will be presented in tabular or graphical format, whichever is deemed most appropriate at the time of reporting the findings.
 
Real-time data capture analysis

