### **3.2.2 Sampling**

Twenty adult participants in the US, and 10 participants in Germany with severe, recurrent nasal polyps who have received nasal polyp surgery in the past 10 years prior to screening will take part in this study. Of these 30 participants, 10 of the 20 US participants (50%) will also complete the real-time data capture app task. The real-time data capture app task will not be conducted in Germany.

In addition to meeting the inclusion/exclusion criteria outlined in section 3.2.1, AV will employ a purposive approach to sampling to ensure patients with a range of demographic, educational and clinical characteristics are recruited. To achieve representation of demographics and clinical characteristics within the sample, sampling quotas will be employed. Overall sampling quotas for the US are detailed in Table 1 and for Germany outlined in Table 2. German demographic data is not collected in regards to ethnicity and race separately, and thus, the quotas have been adjusted to fit the norm in Germany. Quotas may be relaxed if recruitment proves challenging. The clinical and demographic information to support the achievement of these quotas will be captured using the clinician-completed case report form (CRF) and patient-completed demographic form.

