### **Analysis of interviews**

All interviews will be audio-record and transcribed/translated verbatim. All identifiable information (e.g. participants', interviewer's and doctors' names) will be removed from the transcripts to make them anonymous and all participants will be assigned a unique participants identification code (ID).

Qualitative analysis of verbatim transcripts for the semi-structured interviews will be conducted using thematic analysis methods (CE interview data) and framework analysis (CD interview data). All interview data will be audio-recorded, transcribed and entered into ATLAS.Ti, a software package which is designed to facilitate the storage, coding, and analysis of qualitative data. This program allows the researcher to code data at different levels of analysis and search for coded data using Boolean operators. ATLAS.Ti software allows traditional qualitative analysis of transcripts, but facilitates an easier break-down and management of qualitative data into groups and assign 'codes'. Each transcript would be assessed and participant comments that pertain to the main research questions would be highlighted. Axial coding enables the relationship between concepts to be explored.

The AV project leader will review the analysis of the first two interviews with the project researcher and create a coding scheme to be used throughout the analysis process (each highlighted statement will eventually be coded). After analyzing each transcription, the coded statements are then moved into their relevant domains. A list of participant statements would be generated for each domain, all of which will contain a prefix comprising the participant's designated ID number and the corresponding transcript page from which the statement was derived. Of note, whilst the frequency of participants mentioning a particular issue may be reported, quantitative analysis of this data would not occur, since that is not the purpose of qualitative research and the sample sizes are too small to utilize the data meaningfully in a quantitative or statistical fashion.

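### Inclusion item 9 requires full English of every participant, which as written limits the 10-patient German arm to an English-fluent subset and does not fit the arm's evident intent

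*Combined protocol and SAP*

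**What the plan says.** Item 9 of section 3.2.1.1 is "Participant is an English speaker and is able to read, write and fully understand the English language". The synopsis has the same criterion, and so does item 9 of the case report form (CRF) in Appendix 4, where a single negative answer among the inclusion items bars the patient.

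The list is not limited to the US. Section 3.2.1 opens with "Participants eligible for enrolment in the study must meet the following inclusion and exclusion criteria", and section 3.2.1.1 with "Participants will be required to meet the following inclusion criteria to be eligible for inclusion in the study". No exception for Germany appears in the available text.

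The synopsis describes the sample differently: "A sample of 20 US-English speaking patients and 10 German patients will be recruited". On processing of the interviews, section 4 says "All interviews will be audio-record and transcribed/translated verbatim". On sampling, section 3.2.2 says that "the quotas have been adjusted to fit the norm in Germany".

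**The concern.** The criterion looks like US wording that was left unchanged when a German arm was added. Both obvious ways of handling it cause a problem. If recruiters apply it, the German interviews come only from patients selected for full command of English. If they do not, each German participant without full English has been enrolled against a stated inclusion criterion.

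Language is close to what this study measures. Section 2.2 sets out to capture how patients themselves describe their disease, and to test whether they can read and consistently understand the item wording, instructions, response options and recall period of the SNOT-22 and the VAS items. Selecting German patients on English ability weakens that evidence, though it does not remove it. Section 5 offers the section 3.2.1 criteria as a safeguard for a diverse and representative sample. For Germany, item 9 does the opposite, and neither the synopsis nor section 5 lists language selection as a limitation.

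**Working it through.** This is a consistency check on the text. There are no hypotheses (section 3.5) and no endpoints (section 3.3.1), so no error rate or power is involved.

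**The plan's own figures.** Section 3.4: 20 US + 10 German = 30 interviews. Section 4 compares five sets of six for saturation: 5 × 6 = 30. Both agree.

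**Step 1: does item 9 reach Germany?** The body text is enough, without the CRF.
- Section 3.2.1 and the first line of section 3.2.1.1 apply the list to all participants.
- Section 3.2 has both recruitment agencies use one methodology, and an interview is scheduled only if section 3.2.1.1 is met.
- Section 3.2.2 applies the quotas, including Table 2 for Germany, on top of the section 3.2.1 criteria.

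So item 9 binds the German participants.

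**Step 2: does that fit the rest of the plan?**

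| Place | What it shows |
|---|---|
| Synopsis, Study Population | English is attached to the 20 US patients only |
| Synopsis, Data Analysis Methods: interviews are "along with audio real-time data capture app task responses, transcribed/translated verbatim" | Translation is foreseen |
| Section 4, Analysis of interviews | Translation is foreseen for interviews |
| Section 3.2: "The real-time data capture app task will not be conducted in Germany" | App audio is US only |
| Section 3.2.2 and Table 2 | Ethnicity, race and education categories were adapted to Germany; item 9 was not |

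US participants must be English speakers and the app task is confined to the US. The German interviews are therefore the only apparent source of speech that would need translating. Taken together, these places suggest that German patients were not meant to be selected on English. This is an inference: the available text never states the language of the German interviews or of the instruments debriefed there.

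**Step 3: size.**
- Item 9 applied: interviews affected = 10/30 = 33.3% of the study and 10/10 = 100% of the German arm.
- Item 9 not applied: violations = *k*, the number of German participants without full English, with 0 ≤ *k* ≤ 10. That is 0/30 = 0% to 10/30 = 33.3% of the sample.

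The documents give no fluency rate and none is assumed, so *k* cannot be narrowed.

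**The case against.** The strongest reply has four parts.

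1. **The translation wording is soft evidence.** In the synopsis it also covers app audio, which comes only from English-speaking US participants, so it may be stock phrasing. Section 3.3 mentions transcription alone, and section 4 later repeats the step without translation. This stands, and it leaves the contrast in the synopsis sample description as the best sign of intent.

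2. **The appendices look like US versions.** The CRF and the questionnaire booklet go back to the US agency, the demographics form carries only the US quotas, and the interview script promises only the dollar payment although section 3.2 gives German participants euros. Localized German versions may exist, and pages removed before review may state the language. This also stands, so no absence of German materials is claimed and the CRF is not the basis of the point. It does not change the body text of the synopsis or section 3.2.1.1.

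3. **The harm depends on an unknown.** If the German interviews and instruments are in German and local screening ignores item 9, the result is a formal eligibility mismatch and not a loss of evidence. That is fair, but an inclusion criterion should not rely on being disregarded. Appendix 7 also tells the interviewer to check that the criteria are met.

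4. **The study is exploratory and already cautious.** Section 5 admits possible selection bias and disclaims generalization to the wider nasal polyp population. That general caveat does not disclose selection on English ability in one country.

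Nor is the rule impossible to meet: ten English-fluent German patients could fill the places. The restriction would remain.

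**Conclusion.** The concern holds. Item 9 as written limits the whole German arm, 10 of 30 interviews (33%), to patients with full English, and this is inconsistent with the evident intent of that arm. If the rule is not followed, the cost is 0 to 10 eligibility violations. The number of interviews and the saturation sets do not change.

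The reading of the rule rests on the plain text and is secure. The view that the restriction was unintended is an inference. How much German evidence would be affected depends on the interview language and on English fluency, neither of which the available text gives. It should be corrected because the criterion controls entry to an entire country arm.

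**What to change.** First, the sponsor confirms the language of the German interviews and of the SNOT-22 and VAS debriefed in Germany, and states it in section 3.3.

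**If German,** make item 9 country-specific in the synopsis, section 3.2.1.1 and the CRF (or check the German CRF, if a separate one exists). Suggested text: *Participant speaks, reads, writes and fully understands English (US participants) or German (German participants).* The cost is wording in three places plus one statement in section 3.3. German versions of the interview guide, SNOT-22 and VAS must be confirmed as available; if they are not, the cost is more than wording.

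**If English,** keep item 9, say so in section 3.3, and clarify what translation refers to in the synopsis and section 4. Add to the limitations in the synopsis and section 5: *German participants were required to be fluent in English, so the German findings come from an English-fluent subset.* The cost is a few sentences, and the German evidence stays restricted.

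Changing an inclusion criterion may also need review by the two ethics bodies in section 6.1. The documents do not say whether it would.
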